5. ASSESSMENTS

Unless otherwise indicated, all assessments will be performed by the Investigator or designated study personnel.

5.1. Schedule of Assessments

The procedures to be performed throughout the study are outlined in the Schedule of Assessments ([Table 2](#)). A detailed description of each assessment may be found in [Section 5.2](#).

Table 2: Schedule of Assessments

Assessment ▼ Study Day ▶	Screening		Treatment													Follow-up	
	D -42 to -1	D -1	D1	Wk 1	D6	D7±1 ^a	Wk 2	D13	D14±1	Wk 3	D20	D21±1 ^a	Wk 4	D27	EOT ^b D28±1	D55	D56±2 ^c
In clinic visit	x		x			x			x			x			x		x
Informed consent	x																
Medical history	x																
Pulmonary function test	x																
CXR or CT scan ^d	x																
Height and weight ^e	x		x			x			x			x			x		
Physical examination ^f	x		x			x			x			x			x		x
Vital signs ^g	x		x			x			x			x			x		x
12-Lead ECG ^h	x		x						x						x		x
Pregnancy test (females) ⁱ	x		x														x
Urinalysis ^j	x		x			x			x			x			x		x
Blood for safety ^k	x		x			x			x			x			x		x
Blood samples for intense PK ^l			x			x			x			x			x		
Blood samples for sparse PK ^m			x			x			x			x			x		
Blood sample for biomarker ⁿ			x			x			x			x			x		
Patient-collected expectorated sputum ^o		x			x			x			x			x		x	
Induced sputum ^p	x		x			x			x			x			x		x
IP administration ^q			x	x	x	x	x	x	x	x	x	x	x	x	x		
██████████						█			█			█			█		
██████████			█			█			█			█			█		
█ ██████																	
Concomitant medication																	
Adverse events																	

Abbreviations: CT=computed tomography; CXR=chest radiograph; D=day; ECG=electrocardiogram; EOT=end of treatment; h=hour; IP=investigational product; min=minutes; PK=pharmacokinetics; PRO=patient-reported outcome; SOC=standard of care; Wk=week.

- a. As a last resort, with approval from the Sponsor, Days 7 and 21 may be home visits to allow for the collection of induced sputum and blood for PK and safety. Further details will be included in a separate plan.
- b. Patients in open-label SOC Treatment Arm 4 will be discontinued from the study after the EOT visit. For a patient who early terminates and agrees to complete the EOT visit, blood draws for PK will not be conducted. Women of child-bearing potential will have a pregnancy test at this visit.
- c. The follow-up visit will take place 28 days (± 2 days) after the EOT visit for double-blind Treatment Arms 1, 2, and 3.
- d. A CXR or CT scan will be done unless one that is less than 6 months old is available. If obtained at screening, eligibility will be confirmed prior to randomization.
- e. Height required only at screening. Body weight (kg) will be measured at screening and on Days 1, 7, 14, 21, and 28.
- f. Full physical examinations will include the following (at a minimum): skin, head, ears, eyes, nose and throat, respiratory system, cardiovascular system, gastrointestinal system, neurological condition, blood and lymphatic systems, and the musculoskeletal system. Symptom-directed physical examinations will be conducted at study visits on Days 7, 14, 21, and 28.
- g. Vital signs will include systolic and diastolic blood pressure, pulse, temperature, and respiratory rate. Vital sign measurements should be assessed 1 h post-dose (± 15 min). For patients randomized to Treatment Arm 4 (SOC), vital sign measurements can be performed at any time.
- h. On Days 1, 14, and 28, perform the ECG at 1 h post-dose (± 15 min). For patients randomized to Treatment Arm 4 (SOC), ECG can be performed at any time.
- i. A serum pregnancy test will be performed on all women of childbearing potential at screening and Day 1, and, for patients in Treatment Arms 1, 2, and 3, at the follow-up visit 28 days after EOT. On Day 1, serum pregnancy should be confirmed pre-dose.
- j. Microscopic urinalysis will be performed.
- k. Refer to Table 3 for the list of serum chemistry, hematology, coagulation, and calculated creatinine clearance assessments.
- l. Intense PK sampling will take place at selected sites only. On Days 1 and 28: pre-dose (no greater than 1 h prior to dose), post-dose at 1 h (± 5 min), 2 h (± 10 min), 4 h (± 10 min), 8 h (± 15 min), 12 h (± 30 min), and 24 h (± 1 h, but -15 min prior to the next daily dose). On Days 7, 14, and 21: pre-dose (± 1 h) (no greater than 1 h prior to dose), 1 h post-dose (± 30 min), and just before discharge from clinic or at minimum 3 hours post-dose.
- m. Sparse PK sampling will take place at remaining sites. On Days 1, 7, 14, 21, and 28: pre-dose (no greater than 1 h prior to dose), 1 h post-dose (± 30 min), and just before discharge from the clinic or at minimum 3 hours post-dose.
- n. Serum samples for biomarker assessment using the Nanodisk-MS assay will be collected on Days 1, 7, 14, 21 and 28. Biomarker assay will be nanotechnique quantitative detection of NTM specific peptides in serum.
- o. Patient-collected pooled expectorated sputum collected on Days -1 , 6, 13, 20, and 27 (i.e., on the day before clinical study visits over an approximate 24-h period). The patients will bring the pooled samples to the clinic for processing and shipment to the central laboratory.
- p. Respiratory samples using a standard protocol for collecting induced sputum will be used at all sites. Induction will be performed in the clinic with hypertonic saline administered by nebulizer. Induced sputum samples will be collected at screening, and for Treatment Arms 1, 2, and 3 on Day 56 (Follow-up). On Days 1, 7, 14, 21, and 28 sputum samples will be collected pre-dose. Induced sputum samples will be shipped to the central laboratory.
- q. Patients randomized to Treatment Arms 1, 2, and 3 will be double blinded, and Treatment Arm 4 (SOC) will be open label. Dosing for patients in Treatment Arms 1, 2, and 3 will take place at the clinic on study visit days. The clinic and patient should try to schedule clinic visits in the morning as early as possible to accommodate pre-dose study activities and dosing, preferably before a meal. Patients randomized to Treatment Arms 1, 2, and 3 should make every effort to take the IP at the same time in the morning approximately 1 h (no less than 30 min) before a morning meal on an empty stomach. There are no liquid restrictions. Patients will receive a supply of IP and instructions for documenting at-home dosing, which will include the date and time of each IP or SOC dose taken, along with other requested information related to IP administration. Dosing for Treatment Arm 4 (SOC) should occur per specific prescribing information instructions.

█ [REDACTED]

5.2. Screening (Day -42 to -1)

Before enrollment, patients will undergo screening to determine study eligibility. Screening procedures must be performed within 42 days before the first day of treatment (Day 1).

Patients must sign and date the main full study informed consent form (ICF) before any screening procedures are performed.

5.3. Pharmacokinetic Assessments

Blood samples from patients in Treatment Arms 1, 2, and 3 will be obtained for plasma for PK analysis according to the following schedule. Allowable windows of time for the collection of blood samples are shown in the Schedule of Assessments (Table 2).

At 3 or more selected sites, blood samples will be collected from at least 18 patients (at least 6 per treatment arm) for intensive PK evaluation. Intense blood sampling for PK will occur in the clinic on Days 1 and 28 at the following times relative to the time of the daily oral dose administered in the clinic: pre-dose and 1, 2, 4, 8, 12, and 24 h post-dose. On Days 7, 14, and 21, blood samples will be obtained at the following times relative to the time of the daily oral dose administered in the clinic: pre-dose, 1 h post-dose, and just before discharge from the clinic.

At all remaining sites for sparse PK evaluation, on Days 1, 7, 14, 21, and 28, blood samples will be obtained at the following times relative to the time of the daily oral dose administered in the clinic: pre-dose, 1 h post-dose, and just before discharge from the clinic.

Instructions for sample collection, handling, storage, and shipping can be found in the Laboratory Manual.

5.4. Safety Assessments

Physical Examinations: Full physical examinations will be conducted at screening and Day 1, and for patients in Treatment Arms 1, 2, and 3 at the follow-up visit 28 days after EOT. The full physical examination will include, at a minimum, assessment of the following systems: skin, head, ears, eyes, nose and throat, respiratory system, cardiovascular system, gastrointestinal system, neurological condition, blood and lymphatic systems, and the musculoskeletal system. Symptom-directed physical examinations will be conducted at study visits on Days 7, 14, 21, and 28.

Any CS changes from baseline in physical examination findings after dosing will be recorded as AEs. Height without shoes will be recorded at screening.

Vital Signs and Body Weight: Vital signs will be measured at each study visit for systolic and diastolic blood pressure, pulse, temperature (°C), and respiratory rate.

Body weight (kg) will be measured at screening and Days 1, 7, 14, 21, and 28.

Electrocardiogram: Standard 12-lead ECGs will be measured at screening and Days 1, 14, and 28, and, for patients in Treatment Arms 1, 2, and 3, at the follow-up visit 28 days after EOT.

Laboratory Parameters: The following clinical laboratory tests (Table 3) are to be performed as indicated in the Schedule of Assessments (Table 2).

Table 3: Clinical Laboratory Tests

Serum Chemistry	Hematology (CBC)	Urinalysis
Albumin	Hematocrit	Color and clarity
Alkaline phosphatase	Hemoglobin	pH and specific gravity
ALT	Platelet count	Bilirubin
Amylase	RBC count	Protein
AST	RBC indices:	Glucose
Bicarbonate	--MCH	Ketones
Bilirubin (total and conjugated)	--MCHC	Leukocytes
Blood urea nitrogen	--MCV	Microscopy (if clinically indicated):
Calcium (total)	--% Reticulocytes	--Including bacteria, RBCs,
Chloride	RDW	WBCs per HCF
Cholesterol (total)	WBC count	--Sediment
Creatinine	WBC w/differential (% and absolute):	Nitrites
Creatinine kinase	--Basophils	Occult blood
GGT	--Eosinophils	Urobilinogen
Globulins	--Lymphocytes	
Glucose	--Monocytes	
LDH	--Neutrophils	
Lipase		Additional Tests
Magnesium		Serum hCG ^a
Phosphorus		Calculated creatinine clearance using measured serum creatinine with Cockcroft-Gault formula
Potassium		
Protein (total)	Coagulation	
Sodium	aPTT	
Triglycerides	PT	
Uric acid	INR	

Abbreviations: ALT=alanine aminotransferase; aPTT=activated partial thromboplastin time; AST=aspartate aminotransferase; CBC=complete blood count; EOT=end of treatment; GGT=gamma glutamyl transferase; hCG=human chorionic gonadotropin; HPF=high-power field; INR=international normalized ratio; LDH=lactate dehydrogenase; MCH=mean corpuscular hemoglobin; MCHC=mean corpuscular hemoglobin concentration; MCV=mean corpuscular volume; PT=prothrombin time; RBC=red blood cell; RDW=red blood cell distribution width; WBC=white blood cell.

a. Female patients will have a serum pregnancy test at screening and Day 1, and, for patients in Treatment Arms 1, 2, and 3, at the follow-up visit 28 days after EOT.

Laboratory samples will be analyzed by a central laboratory to ensure consistent interpretation of results. Instructions for obtaining and handling laboratory samples are provided in the Laboratory Manual.

In the event of an unexplained clinically noteworthy abnormal laboratory test value, the test should be repeated immediately and followed up until it has returned to the normal range and/or an adequate explanation of the abnormality is found.

Concomitant Medications and Adverse Events: Concomitant medications and AEs will be reviewed and recorded at all study visits. All AEs occurring after the first dose of IP and up to the last study event will be recorded.

See [Section 6](#), for additional information.

5.5. Efficacy Assessments

[REDACTED]

5.6. Appropriateness of Measurements

All assessments to be used in this study are commonly used standard measurements and appropriate for this study in patients with NTM-PD.

6. ASSESSMENT AND MANAGEMENT OF ADVERSE EVENTS

Throughout the course of the study, all AEs will be monitored and recorded in an AE page of the eCRF, including the AE's description, start and end date, seriousness, severity, action taken, and relationship to the IP. If AEs occur, the first concern will be the safety of the study patients. All AEs will be followed until resolved or stable.

6.1. Adverse Event Definitions

An AE is any untoward medical occurrence in a patient or clinical investigation patient administered a pharmaceutical product, which does not necessarily have to have a causal relationship with the treatment. An AE can therefore be any unfavorable and unintended sign (including an abnormal laboratory finding), symptom, or disease temporally associated with the use of a medicinal (investigational/experimental) product, whether related to this product or not. This includes any newly occurring event or previous condition that has increased in severity or frequency since starting active or randomized treatment.

An SAE is any AE occurring at any dose and regardless of causality that:

- Results in death
- Is life-threatening (*Note:* The term "life-threatening" in the definition of "serious" refers to an event/reaction in which the patient was at risk of death at the time of the event/reaction; it does not refer to an event/reaction which hypothetically might have caused death, if it were more severe)
- Requires inpatient hospitalization or prolongation of an existing hospitalization. Hospitalization admissions and/or surgical operations scheduled to occur during the study period, but planned prior to study entry, are not considered AEs if the illness or disease existed before the patient was enrolled in the study, provided that it did not deteriorate in an unexpected manner during the study (e.g., surgery performed earlier than planned).
- Results in persistent or significant disability/incapacity. Disability is defined as a substantial disruption of a person's ability to conduct normal life functions.
- Is a congenital anomaly/birth defect
- Is a medically important event or reaction

Medical and scientific judgment should be exercised in deciding whether other situations should be considered serious such as important medical events that may not be immediately life-threatening or result in death or hospitalization but might jeopardize the patient or might require medical or surgical intervention to prevent one of the other outcomes listed in the above definition. These should also be considered serious. Examples of such events are intensive treatment in an emergency room or at home for allergic bronchospasm, blood dyscrasias or convulsions that do not result in hospitalization, or development of drug dependency or drug abuse. The Investigator must review the laboratory report, document this review, and record any CS abnormal results in the AE section of the eCRF. The laboratory reports will be reviewed, filed, and handled in accordance with the site's source data list.

Clarification should be made between the terms “serious” and “severe” since the terms are not synonymous. The term “severe” is often used to describe the intensity (severity) of a specific event (as in mild, moderate, or severe myocardial infarction); the event itself, however, may be of relatively minor medical significance (such as a severe headache). This is NOT the same as “serious,” which is based on patient/event outcome or action criteria described above and is usually associated with events that pose a threat to a patient’s life or functioning. A severe AE does not necessarily need to be considered serious. For example, persistent nausea of several hours’ duration may be considered severe nausea but not an SAE. However, a stroke resulting in only a minor degree of disability may be considered mild but would be defined as an SAE based on the above noted criteria. Seriousness (not severity) serves as a guide for defining regulatory reporting obligations.

A suspected unexpected serious adverse reaction (SUSAR): An AE or suspected adverse reaction is considered "unexpected" if:

- It is not listed in the IB
- It is not listed at the specificity or severity that has been observed
- The IB is not required or available or not consistent with the risk information described in the general investigational plan or elsewhere in the current application

For example, under this definition, hepatic necrosis would be unexpected (by virtue of greater severity) if the IB referred only to elevated hepatic enzymes or hepatitis. Similarly, cerebral thromboembolism and cerebral vasculitis would be unexpected (by virtue of greater specificity) if the IB listed only cerebral vascular accidents. "Unexpected," as used in this definition, also refers to AEs or suspected adverse reactions that are mentioned in the IB as occurring with a class of drugs or as anticipated from the pharmacological properties of the drug but are not specifically mentioned as occurring with the particular drug under investigation.

Abnormal laboratory findings (e.g., serum chemistry, hematology, coagulation, and urinalysis) or other abnormal assessments (e.g., ECG parameters, vital signs) that are judged by the Investigator as CS will be recorded as AEs or SAEs if they meet the definitions stated above. Clinically significant abnormal laboratory findings or other abnormal assessments that are detected during the study or are present at baseline and significantly worsen following the first dose will be reported as AEs or SAEs. The Investigator will exercise his/her medical and scientific judgment in deciding whether an abnormal laboratory finding or other abnormal assessment is CS.

6.2. Evaluating Adverse Events and Serious Adverse Events

6.2.1. Assessment of Intensity

The Investigator will assess the intensity for each AE and SAE reported during the study. The assessment will be based on the Investigator’s clinical judgment using the latest version of the National Cancer Institute Common Terminology Criteria for Adverse Events (CTCAE) v5.0 as a guideline, wherever possible. The intensity of each AE and SAE recorded should be assigned to one of the following categories:

- **Mild:** An event that is easily tolerated by the patient, causing minimal discomfort and not interfering with everyday activities
- **Moderate:** An event that is sufficiently discomforting to interfere with normal everyday activities
- **Severe:** An event that prevents normal everyday activities. An AE that is assessed as severe should not be confused with an SAE. Severity is a category utilized for rating the intensity of an event; and both AEs and SAEs can be assessed as severe
- **Life-Threatening or Disabling:** An event that poses an immediate risk of death from the reaction as it occurred
- **Death:** The event resulted in death

The following terms and definitions are used in assessing the final outcome of an AE:

- **Recovered/Resolved:** The patient has fully recovered, or by medical or surgical treatment, the condition has returned to the level observed at the first study-related activity after the patient signed the informed consent
- **Recovering/Resolving:** This term is only applicable if the patient has completed the study or has died from another AE, the condition is improving, and the patient is expected to recover from the event
- **Recovered/Resolved with Sequelae:** The patient has recovered from the condition, but with lasting effect due to a disease, injury, treatment, or procedure. If a sequela meets an SAE criterion, the AE must be reported as an SAE
- **Not Recovered/Not Resolved:** The condition of the patient has not improved, and the symptoms are unchanged, or the outcome is not known at the time of reporting
- **Fatal:** This term is only applicable if the patient died from a condition related to the reported AE. Outcomes of other reported AEs in a patient before he/she died should be assessed as “recovered/resolved,” “recovering/resolving,” “recovered/resolved with sequelae,” or “not recovered/not resolved.” An AE with fatal outcome must be reported as an SAE
- **Unknown:** This term is only applicable if the patient is lost to follow-up

6.2.2. Assessment of Causality

The Investigator (or designee) will make an assessment as to the relationship between the study drug and the occurrence of each AE/SAE. The Investigator (or designee) will use clinical judgment to determine whether the AE/SAE is causally related to the study drug. Alternative causes, such as natural history of the underlying diseases, concomitant therapy, other risk factors, and the temporal relationship of the event to the study drug will be considered and investigated. The Investigator (or designee) will also consult the IB in the determination of his/her assessment.

The causal relationship of the study drug to an AE will be rated according to the following 4-point scale:

- **Unrelated:** Clearly and incontrovertibly due only to extraneous causes and does not meet criteria listed under unlikely, possible, or probable
- **Unlikely:** Does not follow a reasonable temporal sequence from administration; may have been produced by the patient's clinical state or by environmental factors or other therapies administered
- **Possible:** Follows a reasonable temporal sequence from administration; may have been produced by the patient's clinical state or by environmental factors or other therapies administered
- **Probable:** Clear temporal association with improvement on cessation of study drug or reduction in dose; reappears upon rechallenge or follows a known pattern of response to the study drug

There may be situations when an SAE has occurred and the Investigator (or designee) has minimal information to include in the initial report to the Sponsor. However, it is very important that the Investigator (or designee) always assess causality for every event before transmission of the SAE form to the Sponsor. The Investigator (or designee) may change his/her opinion of causality in light of follow-up information, amending the SAE form and the eCRF accordingly. The causality assessment is one of the criteria used when determining regulatory reporting requirements. The Investigator (or designee) will provide an assessment of causality as per instructions on the SAE form.

6.3. Time Period, Frequency, and Method of Detecting Adverse Events

As a consistent method of soliciting AEs, the patient shall be asked a nonleading question such as: "How do you feel?"

Any preexisting conditions or signs and/or symptoms present in a patient before the start of the study (e.g., before informed consent) should be recorded as medical/surgical history. In addition, any change in health status, which is reported after informed consent is obtained but before receipt of study drug, will be documented as medical/surgical history.

Any medical occurrence reported or observed after the first dose of study drug will be recorded as an AE. Adverse events will be evaluated by the Investigator (or designee) and recorded.

Any AEs already documented at a previous assessment and designated as ongoing, should be reviewed at subsequent assessments, as necessary. If these have resolved, this should be documented.

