6.4. Adverse Event Management

The Investigator (or designee) will provide appropriate medical care for the clinical management of any AEs related to study participation, whether identified during or after the course of study participation. Evaluation and treatment of any AE (or CS laboratory abnormality) is at the discretion of the Investigator based on their clinical judgment. The applied measures should be recorded in the patient's source documents and entered in the eCRF as applicable. Referral or collaborative care will be organized if considered necessary by the Investigator. As noted in

Section 6.7, the Sponsor may request additional supplemental investigations as needed to elucidate the nature and/or causality of an SAE.

Serious AEs will be reported to competent authorities in accordance with national requirements.

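### AE and SAE recording starts at the first dose, after two mandated hypertonic-saline inductions, so a serious harm from either has no mandatory report

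*Combined protocol and SAP*

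**What the plan says.** **When recording starts.** Section 6.3 sends any health change after consent "which is reported after informed consent is obtained but before receipt of study drug, will be documented as medical/surgical history". The same section continues: "Any medical occurrence reported or observed after the first dose of study drug will be recorded as an AE". Section 5.4 sets the same start: "All AEs occurring after the first dose of IP and up to the last study event will be recorded". Section 4.7.1 likewise makes a new illness an AE only once dosing has begun.

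**What counts as serious.** Section 6.1 builds the SAE on the AE: "An SAE is any AE occurring at any dose and regardless of causality that" meets one of the listed criteria. Section 6.6.2 then requires SAEs to be reported within 24 h. No section gives SAEs an earlier start of their own.

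**What is done to patients before the first dose.** Table 2, footnote p, says of sputum collection: "Induction will be performed in the clinic with hypertonic saline administered by nebulizer". It schedules an induction at screening and adds: "On Days 1, 7, 14, 21, and 28 sputum samples will be collected pre-dose". Inclusion criterion 5 makes the screening induction a condition of entry.

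**Broader wording elsewhere.** The opening of section 6 has AEs monitored and recorded over the whole study. Section 6.1 treats clinically significant abnormal findings picked up during the study as AEs or SAEs. Section 8.1.9.2 says that all AEs in the study are recorded, and defines the TEAE separately by the first dose. Section 6.6.2 asks for any event that the investigator thinks could threaten the patient's health to be passed to the sponsor's medical representative or emergency contact. None of these four places carries the first-dose limit on recording or reporting.

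**The concern.** The interval between consent and first dose is not a period of passive observation. The trial performs a procedure on patients in it, twice, and inclusion criterion 9 admits patients with a percent predicted FEV1 as low as 30%. The protocol itself names bronchospasm needing intensive emergency treatment as an example of an important medical event (section 6.1). If that followed the screening or Day 1 induction, sections 6.3 and 5.4 would make it history rather than an SAE. It would then get no causality assessment, no 24 h report, no required follow-up under section 6.7 and no place in the safety summaries.

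Two further rules widen the gap. Section 4.7.2 keeps treatments given before the first dose out of the eCRF, although its closing sentence reads more broadly. The causality scale in section 6.2.2 rates only the study drug, so a procedure as cause has no category.

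What is at stake is participant safety, and how quickly a problem with a repeated, mandatory procedure would be recognised.

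**Working it through.** The plan states no figure on this point, so there is none to reproduce. The check has three parts.

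**1. Does the SAE duty start before the first dose?**
- Sections 6.3 and 5.4: an event becomes an AE only after the first dose.
- Section 6.1: an SAE is an AE that meets a seriousness criterion.
- Section 6.6.2: the 24 h report applies to SAEs.

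Taken together, the mandatory report starts at the first dose. The broader wording in section 6, section 6.1 and section 8.1.9.2 points the other way but gives no start date, whereas 6.3 deals with the pre-dose interval expressly. A site could cite either.

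**2. How many inductions fall outside the window?** Inputs: Table 2 and footnote p for the visits; section 3.1 for 90 patients and 15 to 16 in Arm 4 (intense PK sites do not randomize to Arm 4).
- Arms 1 to 3: screening, Days 1, 7, 14, 21, 28 and 56 = 7 per patient.
- Arm 4: the same without Day 56 = 6 per patient.
- Before the first dose, all arms: screening + Day 1 = 2 per patient.

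| Arm 4 size | Scheduled inductions | Before first dose | Share |
|---|---|---|---|
| 15 | 75 × 7 + 15 × 6 = 615 | 90 × 2 = 180 | 180/615 = 29.3% |
| 16 | 74 × 7 + 16 × 6 = 614 | 90 × 2 = 180 | 180/614 = 29.3% |

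This assumes that all 90 attend every scheduled visit and that none is rescreened. Section 3.3.6 allows rescreening, which would add pre-dose inductions. Screen failures who were induced come on top; the documents do not say how many there would be.

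**3. How likely is it that something is missed?** The documents give no event rate for induction. As an illustration only, assume a risk p per induction, independent across inductions. The expected number of events is 180p, and the chance of at least one is 1 − (1 − p)^180.

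| Assumed p | Expected pre-dose events | Chance of at least one |
|---|---|---|
| 0.1% | 0.18 | 16% |
| 0.5% | 0.9 | 59% |
| 1% | 1.8 | 84% |
| 5% | 9.0 | >99% |

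Even at the lower assumed rates the chance of at least one event is not negligible, but which row applies cannot be settled from the documents.

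**The case against.** The strongest reply is that a reader might infer that such harms are never reported, and the documents do not support that. The sentence in 6.6.2 on events of concern is limited neither to AEs nor to the time after dosing, and a hospital admission for bronchospasm plainly fits it. The event is also entered as medical history (section 4.7.1). This stands, and it limits the point to the lack of a mandatory route: the sentence turns on the investigator's opinion and carries no deadline, causality rating or follow-up of its own.

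A second reply is that the procedure is still watched. The other 434 to 435 inductions (71%) fall inside AE recording, and a pre-dose condition that worsens after the first dose becomes an AE. It also stands that a pattern of harm would not be wholly invisible. It does not help the individual pre-dose event, or screen failures, who never enter the window.

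Other stronger readings should be set aside:
- Section 6.4 does not contradict 6.3. Its promise of "clinical management of any AEs related to study participation, whether identified during or after the course of study participation" concerns medical care, not when recording starts.
- Exclusion criteria 17 and 18 do not impose a washout. They exclude patients who took listed drugs.
- A total that includes screen failures can be built. With an assumed failure rate of 30% to 50%, 90/0.7 = 129 to 90/0.5 = 180 patients are screened, and adding 90 Day 1 inductions gives 219 to 270. But neither that rate nor the assumption that every screened patient is induced comes from the documents.
- The 42-day screening period as a share of study time (42/98 = 43% in Arms 1 to 3, 42/70 = 60% in Arm 4) measures calendar time, not exposure to the procedure.

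Finally, the marks in the adverse-event row of Table 2 cannot be read in the public copy and section 5.5 is blacked out, so the absence of any other provision cannot be certain.

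**Conclusion.** The point holds as a gap in mandatory safety reporting. Under sections 6.3 and 5.4, read with the SAE definition in 6.1, harms from two mandated inductions per dosed patient are not classed as AEs or SAEs, get no causality rating and have no required 24 h report. The document-based size is 180 of 614 to 615 scheduled inductions (29%), assuming 90 patients complete the schedule with no rescreening, plus an unknown number in screen failures. The first-dose rule also does not match the broader wording in the opening of section 6, in 6.1 and in 8.1.9.2.

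It should not be read as a threat to the trial's results. The primary PK endpoints and the by-arm TEAE summaries are unaffected, because the TEAE definition is properly tied to the first dose. Severity: should-fix.

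**What to change.** Reconcile 5.4, 6.3 and 6.6 with the opening of section 6, with 6.1, 6.6.2 and 8.1.9.2, so that all state one window:

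- From signed consent, record all SAEs and report them within the existing 24 h limit.
- From signed consent to first dose, also record any non-serious AE judged related to a protocol-required procedure.
- Apply both to screen failures.
- Enter treatments given for such events, as an exception to the pre-dose rule in 4.7.2.
- Keep the TEAE definition in 8.1.9.2 as it is and show pre-dose events in a separate listing, so that no by-arm table changes.

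The cost is modest but more than a change of wording. Sites enter a few more pre-dose records. A procedure-relatedness assessment is needed, since 6.2.2 covers the study drug only. Screen failures need an identifier, since section 4.3 assigns the patient number at randomization.
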